5. Report having consumed at least one alcoholic drink during a minimum of 12 days out of the prior 30 in order to maximize the likelihood that subjects will choose to drink during the self-administration portion of the laboratory sessions.*
6. Meet, at minimum, DSM-5 criteria for a mild alcohol use disorder (i.e., meet at least 2 diagnostic criteria)
7. Perform within 2 standard deviations of normative levels both with regard to reaction time and number of errors on the cued go/no-go task at in-person screening.

8. Have an iPhone/iOS-compatible phone that they are willing to use for study-related tasks (field use-only participants from outside of the Gainesville area, only; local participants will have an opportunity to borrow a study phone)

Exclusion Criteria:

No subject may:

1. Be seeking treatment for alcohol or other addictive behaviors or have been in inpatient or intensive outpatient treatment within the past 12 months
2. Have used a smartphone application to facilitate moderate drinking more than 1 time within the past 12 months
3. Provide two positive breath alcohol concentration (BrAC) readings (i.e., > 0.00%) at an in-person screening appointment or on the day of the alcohol drinking session. After participants blow their first positive BrAC, they will be allowed to reschedule and participate at another time, however if they blow a second positive BrAC, they will be excluded from this study and offered referrals for alcohol treatment. **
4. Have positive urine screen results at the in-person screening or on the day of an alcohol drinking session for opiates, cocaine, phencyclidine, amphetamines, methamphetamine, barbiturates, methadone or benzodiazepines. **
5. Meet criteria for current moderate or severe DSM-V Cannabis Use Disorder, or a mild, moderate, or severe DSM-V substance use disorder on any other drug, excluding alcohol.
6. Report current use of psychotropic drugs including anxiolytics and antidepressants. **
7. Have received a prescription for any psychotropic drug in the 30 days prior to study enrollment **
8. Be psychotic or otherwise severely psychiatrically disabled
9. Report a history of a medical condition that would contraindicate the consumption of alcohol (e.g., liver disease, cardiac abnormality, pancreatitis, diabetes, neurological problems, and gastrointestinal disorders).

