We will collect data for 4 weeks as people engage in usual drinking. The app will be programmed to deploy the CGNG, give related feedback and offer advice for 2 of the 4 wks (counterbalanced), enabling within-subject comparison of alcohol use with vs. without the main component app. The app will prompt 3 times on typical drinking days. Participants can set the app to prompt on other days also. After CGNG and feedback, participants report perceived impairment, the number of standard drinks they have consumed to that point and the extent to which they want and would like more alcohol. During the 2-weeks when the app does not deploy the CGNG task and feedback, participants will answer the questions only. Each morning for the 4 weeks, the app will prompt recording of number of drinks and time spent drinking the prior day. Data collected by the app will not be visible after it is submitted so minimal information about participants will be visible in the app if the phone is stolen, lost, "hacked" or in some other way made visible to another person. Even though task performance and self-report responses are no longer visible after submission we suggest that all participants password protect their phone, and change the auto lock to 1 minute so that the application cannot be accidentally accessed by anyone other than the study participant. Participants completing only the field use period will attend a baseline appointment, which can be held remotely via a password-protected UF Zoom meeting. During this baseline appointment participants will be walked through how to download the smartphone application, and shown how to use the app. They will be asked to use the app during the appointment to gather baseline data, and will then be pinged again later that evening or the following morning to use the app again. Compensation for this appointment will be \$10. Following their baseline appointments participants will be asked to attend an orientation appointment where they will receive their randomized version of the smartphone application. They will receive \$10 for this appointment. Participants completing lab sessions will complete these appointments in the course of their session participation and receive the same

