Eligibility Checklist: This checklist is used by study staff to determine participant eligibility based on measures taken during the screening appointment to make certain that active evaluations of eligibility and ineligibility are made.

Screening and at Alcohol Administration Sessions:

Breath alcohol concentration: Breath alcohol concentration will be assessed using a hand-held Intoxilyzer breathalyzer unit at the in-person screening; at the preliminary appointment earlier on the day of the alcohol drinking session; at the outset of the alcohol drinking session and then at several points during the sessions.

Alcohol purchase task: This is a simulation measure to assess self-reported alcohol consumption and expenditure were alcohol to cost varying amounts of money. The measure generates a number of variables pertaining to reinforcement from alcohol, including intensity of demand. The purchase task will be administered twice during the in-person screening appointment. One version will assess how many drinks a participant would consume right now at varying amounts of money and a modified version will assess how many drinks a participant would consume on a hypothetical weekend evening. At the alcohol drinking session, the “right now” version of the measure will be administered multiple times at both at baseline and after the drinking period. This will allow a comparison of the amounts of hypothetical money participants are willing to spend on alcohol, a priori, upon arrival at the bar or simulated lab and after consumption of alcohol.

Risk Taking Behavior: The *Cognitive Appraisal of Risk Events* (CARE) and its revised version (CARE-R; Katz, Fromme, & D'Amico, 2000) assess recent negative consequences and expectations that these consequences will occur again in the near future. Of the measure's 4 subscales, we will administer at in-person screen a version of the past frequency subscale that combines the original with the revised version in order to obtain baseline data. Participants will be asked to report how many times in the past 3 months each has occurred. Then after fixed dose in the individual session, we will administer the expected involvement subscale. Items are rated a 7-point Likert scale ranging from “not at all likely” to “extremely likely”.

Alcohol Administration Sessions:

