Normal probability plots will be reviewed to assess normality and need for transformations. Paired samples *t*-tests will be used to confirm an effect of initial dose on CGNG inhibition errors but not RT. Our analytic strategy will resemble 3 past studies. The main method will be multiple regression with study condition and sex as predictors. Baseline variables that differ significantly by condition will be covaried.

Outcome 1a will be BAC during self-administration. Because we will not interrupt alcohol self-administration with BrAC readings, we will calculate peak estimated BAC (eBAC) based on number of alcoholic drinks, time elapsed, weight and sex. eBAC was sensitive to differences in consumption between study conditions in a prior study conducted by [name]. Results will be BrAC-confirmed after the 1-hr free-drinking period. Though not the main focus, we will test 2-way interactions of study condition by RT and inhibition errors post-alcohol to see if more inhibition failures under alcohol predict self-administration. Regressions will be confirmed using multilevel models (MLM) in Mplus with random effect of group (people completing a drinking session together) and other predictors as fixed effects. Since participants will be randomized to different apps, we do not expect strong intra-class correlations, which should result in similar findings in regression and MLMs. In our in-progress study, no group level effects have emerged. A similar strategy will be used for 1b (alcoholic drinks self-administered).

Primary Aim 2 will entail comparisons of alcoholic drinks consumed per occasion between the 2 weeks participants will use vs. not use the app in the 4-week field period post-drinking session. We will retain study condition as a predictor (effects of lab-assigned condition are not hypothesized here) and a random group effect while adding app use vs. non-use period as a within-subjects effect in MLM. ANOVA will compare usability and acceptability ratings at the end of the drinking session and 4-week field period across app conditions. For mediation (Secondary Aim), we will test for indirect effects of app condition on self-administration via perceived impairment using MacKinnon’s products of coefficients approach with bootstrapped confidence intervals (CIs). This approach accounts for non-normality of the product of

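### The Primary Aim 2 model has no day-of-week term, so it forgoes a small, cheap gain in precision; the participant-level random effects should be stated at the same time

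*Combined protocol and SAP*

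**What the plan says.** The Data analyses section sets Primary Aim 2 as "comparisons of alcoholic drinks consumed per occasion between the 2 weeks participants will use vs. not use the app". The model retains lab condition and a random effect for drinking group, "adding app use vs. non-use period as a within-subjects effect in MLM". No weekday term is named. Nor does the section say whether the rows are days, drinking occasions or participant-period means. No participant random intercept or random slope for period is named, although calling period a within-subjects effect implies a participant level.

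Post-session field use describes the app as programmed to "give related feedback and offer advice for 2 of the 4 wks (counterbalanced), enabling within-subject comparison". It also provides daily data: "Each morning for the 4 weeks, the app will prompt recording of number of drinks and time spent drinking the prior day". Two other places touch on when people drink. Post-session field use says "The app will prompt 3 times on typical drinking days", and the alcohol purchase task at screening has a second form: "a modified version will assess how many drinks a participant would consume on a hypothetical weekend evening".

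Sample, power & effect size gives the Aim 2 sensitivity as a within-subject effect of .33 at alpha .05, 90% power and 99 participants.

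**The concern.** If young adults drink more per occasion on Fridays and Saturdays than on other days, part of the day-to-day variation within a person is predictable from the date. A model without weekday treats that part as noise. The outcome is defined only on drinking days, so one person's app-on block may by chance contain more weekend occasions than the app-off block. That difference then moves the app estimate. The weekday is available for every row at no extra cost, and the comparison is a primary aim. What is at stake is precision, not validity: without the term the app effect is estimated somewhat less sharply than the collected data allow.

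**Working it through.** **1. The plan's own figure.** A two-sided paired comparison on 99 participant differences gives (1.960 + 1.2816)/√99 = 3.2415/9.950 = 0.326. The noncentral t with 98 df gives 0.329, and power at .33 is 0.902. The stated .33 reproduces. It is in units of the SD of participant differences, so a weekday term does not alter it.

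**2. Inputs.** From the documents: N = 99, 28 days, two weeks on and two off, and entry requiring "at least one alcoholic drink during a minimum of 12 days out of the prior 30". At that minimum, 12/30 × 14 = 5.6 occasions fall in a block. Assumed, because the documents give none of them: probability of drinking .85 on Friday and Saturday and .30 on other days; person SD 2; within-person SD σ of 2, 2.5 or 3 drinks; weekend excess δ of 1, 2 or 3 drinks. These probabilities give 8 × .85 + 20 × .30 = 12.8 occasions in 28 days, or 6.4 per block.

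**3. How much weekday variation reaches the estimate.** Per block, weekend occasions have mean 4 × .85 = 3.4 and variance 4 × .85 × .15 = 0.51. Other occasions have mean 10 × .30 = 3.0 and variance 10 × .30 × .70 = 2.1. The weekend share of occasions then has variance of about (3.0² × 0.51 + 3.4² × 2.1)/6.4⁴ = 28.87/1677.7 = 0.0172. On the scale of a single row this adds 6.4 × 0.0172 × δ² = 0.110δ² to σ².

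The residual of an unadjusted row-level model instead absorbs (6.8/12.8)(6.0/12.8)δ² = 0.249δ². So about 0.110/0.249 = 44% of the weekday variance truly affects the estimate. The other 56% only inflates the reported standard error.

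**4. Gain in true precision.** The ratio of true sampling SDs, with versus without the term, is √[σ²/(σ² + 0.110δ²)], assuming the app effect is the same for everyone.

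| Assumed excess δ | Reduction by formula, σ = 3 to 2 | Reduction by simulation |
|---|---|---|
| 1 drink | 0.6% to 1.3% | about 1-2% |
| 2 drinks | 2.4% to 5.1% | about 2-7% |
| 3 drinks | 5.1% to 10.5% | about 3-10% |

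A reduction r is worth 1/(1 − r)² − 1 more participants: 2% for r = .01, 4% for .02, 6% for .03, 16% for .07 and 23% for .10. If standard errors are honest both with and without the term, an effect with 90% power without it has power Φ(3.2415/(1 − r) − 1.96) with it. That is about 91% at r = .02, 94% at r = .07 and 95% at r = .10.

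**5. Are the unadjusted error bars wrong, and in which direction?** Reported standard error divided by true SD:

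- Occasion rows, same app effect in everyone: √[(σ² + 0.249δ²)/(σ² + 0.110δ²)], from 1.008 (δ = 1, σ = 3) to 1.118 (δ = 3, σ = 2). Simulation gave 0-15% too wide.
- Participant-level paired differences: 0.97 to 1.03, so no inflation.
- Occasion rows, app effect varying between people (SD 0.3 of the within-person SD), no random slope, weekday share of within-person variance 10-50%: 0.90 to 1.00 without the term and 0.81 to 0.89 with it. With an assumed app-effect SD of 1 drink: 0.78 to 0.94 without and 0.77 to 0.88 with.

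In the last case the standard error is too narrow, and a weekday term alone narrows it further.

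**The case against.** A reader might infer that each block holds every weekday twice, so that weekday is balanced and its omission simply makes the error bars too wide. The documents do not support that. Calendar days are balanced if the blocks are whole weeks, but the outcome is per occasion and participants choose when to drink. The row level and random effects are unstated. On participant differences, the basis that reproduces .33, the standard error is honest without the term. With a varying app effect and no random slope it can be too narrow. That objection stands in full.

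A reader might also size the gain by the fall in the reported standard error, which at a 3-drink excess is 11-21% in simulation. Much of that fall only corrects a conservative standard error; the true gain is about 3-10%.

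The evidence for a weekday pattern is indirect. The prompting rule concerns when people drink rather than how much, and the weekend purchase task is a hypothetical screening measure. At a 1-drink excess the gain is negligible. Finally, if the app shifts which days people drink, conditioning on weekday changes what the contrast estimates. This is a fair but minor point, which an unadjusted sensitivity analysis meets.

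What remains is that an honest standard error need not be an efficient one. The gain in true precision persists on occasion rows and, after adjustment for weekend mix, on paired means (2-6% at 2 drinks, 5-12% at 3).

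**Conclusion.** The concern holds as a missed, inexpensive gain in precision. The true sampling SD of the app effect would fall by about 1-2%, 2-7% or 3-10% for an assumed weekend excess of 1, 2 or 3 drinks with a within-person SD of 2 to 3. The excess, drinking probabilities and SDs are all assumptions. There is no bias, no invalid test and no change to the stated .33. It cannot be said that the planned error bars are too wide: the direction depends on a random-effects structure that the plan leaves open. That structure should be settled together with the weekday term, because adding the term alone could worsen an already narrow standard error. Label: cheap improvement.

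**What to change.** In the Data analyses paragraph for Primary Aim 2, state that:

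- the rows are drinking days, dated from the morning report of the prior day;
- the model has a participant random intercept and a random slope for app period (or participant-clustered standard errors), besides the lab condition and group terms already planned;
- day of week enters as a pre-specified fixed effect, either Friday/Saturday versus other or seven levels;
- the app-on versus app-off contrast remains the test;
- the same contrast without the weekday term is reported as a sensitivity analysis.

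The cost is a few lines of text, one to six parameters for weekday and no new data. The adjusted contrast becomes a within-weekday comparison if the app changes which days people drink, which is why the unadjusted result should appear beside it. The choice should be fixed before the field data are examined, since adding weekday afterwards would be a discretionary choice on a primary aim.

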Hypothesis: Participants will self-administer less alcohol when using the experimental app with feedback.

Secondary Aim: Test increased perceived impairment as a partial mediator of the effects in the prior Aims.

Hypotheses: Participants using the experimental app will report higher perceived impairment, which will mediate relations between app use and lower alcohol consumption in the lab and in the 4-week post period.

Exploratory Aim 1: Test study condition during the lab sessions, amount of alcohol self-administered (operationalized as estimated peak BAC and number of drinks self-administered in separate models) in the group alcohol drinking session and during the field period in the intervention and non-intervention periods as predictors of self-reported alcohol consumption (e.g., drinks per drinking day) and alcohol-related problems self-reported at 6- and 12-months post-session on web-based surveys.

Exploratory Aim 2: Test BACTrack Skyn readings taken during each alcohol administration session as predictors of successive breath alcohol readings taken following alcohol administration/self-administration periods in the alcohol drinking sessions and to predict number of drinks self-administered during the group drinking session.

[figure not shown]
Exploratory Aim 3: Predict scores on self-reported expected involvement in risky behaviors post-alcohol administration based on performance on the app-based cued go/no-go task following a .06% fixed alcohol dose in each alcohol drinking session.

6. Research Plan

Overview

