Preliminary steps: Participants will be asked not to eat for 3 hours pre-arrival. Alcohol drinking will occur in a bar lab located at Yon Hall North in Ben Hill Griffin Stadium at the University Florida campus. Participants will be brought to the bar or simulated laboratory for the session via study-provided transportation: either a professional service such as taxi or Uber or a UF-owned automobile driven by a UF employee. However, if a participant lives within a 0.5-mile radius of the research facility they may walk to the facility rather than being driven. These participants may be walked home by study staff after the end of the alcohol drinking session. Upon arrival, BrAC must=0.00% and urine tests will be repeated. Participants registering a BAC > 0.00% or with a positive urine test that leads to exclusion will be dismissed immediately and provided transportation directly home by the study. Participants will complete US-THRIVE, an efficacious, brief, web intervention based on M.I. (i.e., personalized feedback on drinking patterns, behavioral strategies, alcohol facts and resources). Before the alcohol administration, participants may be asked to wear the BACTrack Skyn alcohol wristband monitor, which looks like a fitness tracker or wristwatch and can detect alcohol as it evaporates through the skin. Prior to the session, they will be randomized to 1 of the 3 app conditions. The randomization procedure will be managed by a study staff member/collaborator without direct participant contact. Staff working with participants will not know app assignment.

Instructions: After participants learn their app condition, they will view a presentation on the CGNG and how to use their assigned app. They will be told the app is based on a cognitive game and that they will use it 3 times. They will learn that the task is relevant to real-life as moderate amounts of alcohol affect task success and poor performance has been linked to driving problems and risky decisions. [name] has used similar instructions relating alcohol to task performance and pay^{65, 66} and seen a range of alcohol use in lab drinking sessions.

Alcohol administration steps: After completing US-THRIVE and using the app, the participant will be given vodka mixed drinks targeting a BAC of .06% based on sex, height, and weight divided into three parts. The participant will have 10 minutes to complete each drink and after

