coefficients in calculating indirect effects of IV on DV, operating through a mediator. When the CI does not include 0, an indirect effect is significant at the specified alpha level.

For Exploratory Aim 1, we will test between-subjects study condition during the lab sessions, amount of alcohol self-administered (operationalized as estimated peak BAC and number of drinks self-administered in separate models) in the alcohol drinking session and during the field period in the intervention and non-intervention periods as predictors of self-reported alcohol consumption (e.g., drinks per drinking day) and alcohol-related problems self-reported at 6- and 12-months post-session on the web-based surveys using MLM. Baseline reports of each alcohol-related outcome and participant sex will be entered as covariates. The web-based surveys at baseline, 6- and 12-months post also include measures of several potential covariates that may be entered into these models should they differ significantly across study conditions.

For Exploratory Aim 2, we will use separate MLMs to test BACTrack Skyn readings during each alcohol administration session as predictors of successive breath alcohol readings taken following alcohol administration/self-administration periods in the alcohol drinking sessions and to predict number of drinks self-administered during the group drinking session. Sex and participant weight will be entered into these models as covariates as well.

For Exploratory Aim 3, we will use MLM to predict expected involvement scores on the CARE measure post-alcohol administration based on performance on the app-based cued go/no-go task following the .06% fixed dose as the predictor variable. Baseline expected involvement scores and scores on the other CARE subscales will be held constant in these models. Since the .06% dose will be administered at each session along with cued go/no-go task performance and the CARE, these measures will be entered into the same models as repeated measures. Participant sex and study condition will also be entered as covariates in these models

Sample, power & effect size

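### As most naturally read, Exploratory Aim 1 adjusts randomised lab condition for drinking measured after randomisation, so the condition coefficient is not the total effect at 6 and 12 months

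*Combined protocol and SAP*

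**What the plan says.** The combined protocol and SAP states Exploratory Aim 1 in section 5 (Specific Aims) and again under Data analyses in section 6. The aim opens "Test study condition during the lab sessions, amount of alcohol self-administered", and the analysis text repeats it as "we will test between-subjects study condition during the lab sessions, amount of alcohol self-administered". A parenthesis says the amount is "operationalized as estimated peak BAC and number of drinks self-administered in separate models". The same list goes on to drinking "during the field period in the intervention and non-intervention periods as predictors of self-reported alcohol consumption", and the outcomes include "alcohol-related problems self-reported at 6- and 12-months post-session on the web-based surveys using MLM". For adjustment the plan says "Baseline reports of each alcohol-related outcome and participant sex will be entered as covariates", with other baseline measures possibly added if they differ across conditions.

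Three other places matter:

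- On timing, the individual drinking session section says "Prior to the session, they will be randomized to 1 of the 3 app conditions". Lab and field drinking therefore both follow randomisation.
- The hypothesis attached to the primary aims is "Participants will self-administer less alcohol when using the experimental app with feedback".
- The group session section says that all participants receive the experimental app for the field period, whichever version they used in the lab.

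No model with condition but without the drinking measures is described for the 6- and 12-month outcomes. The planned product-of-coefficients mediation analysis concerns perceived impairment only.

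**The concern.** The parenthesis about separate models divides the two versions of the drinking measure. It does not divide condition from drinking. Read that way, each model contains randomised condition together with a variable that the trial expects condition to change.

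The condition coefficient then no longer estimates what randomisation identifies. Any lasting effect that runs through lower lab drinking is taken out. In addition, conditioning on lab drinking links condition to whatever unmeasured tendency drives both lab and later drinking. If heavier lab drinkers also tend to drink more later, both shifts go against the experimental app.

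This aim holds the only planned test of lab condition at 6 and 12 months. As written, no planned result would give the total randomised effect there.

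**Working it through.** **The plan's own figure.** Exploratory Aim 1 has no power or effect-size statement. The relevant figure is for Aim 1: d=.89, alpha .025, 33 per condition, power .90 (Sample, power & effect size). A two-sample t-test with two-sided alpha .025 has noncentrality .89 x sqrt(33/2) = 3.62 and power .904, so the figure reproduces. I use d=.89 as the effect of condition on lab drinking.

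**Model.** X = 1 for the experimental app and 0 for a comparison version; M = lab drinking; Y = later drinking; U = an unmeasured drinking tendency. M and Y are in within-arm SD units, and negative values favour the app.

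- M = -.89 X + lam U + error
- Y = b M + c' X + g U + error

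The documents give no value for b, c', lam, g, or for r (the correlation of the baseline covariate with U). All are assumptions.

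**Formulas for the coefficient of X.**

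- Condition-only model: c' - .89 b, the total effect.
- Joint model without a baseline covariate: c' + .89 g lam. The shift from the total effect is .89 (b + g lam).
- Joint model with the baseline covariate: c' + .89 g lam (1 - r^2) / (1 - lam^2 r^2).

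The last term, with r=.7:

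- Loadings .5: .89 x (.25 x .51)/(1 - .25 x .49) = .89 x .1275/.8775 = .13
- Loadings .3: .89 x (.09 x .51)/(1 - .09 x .49) = .89 x .0459/.9559 = .04

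**Results (SD of later drinking).**

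| Assumptions | Condition-only | Joint |
|---|---|---|
| b=.35, c'=0, no common cause | -.31 | 0.00 |
| b=.35, c'=0, loadings .5, r=0 | -.31 | +.22 |
| b=.35, c'=0, loadings .5, r=.7 | -.31 | +.13 |
| b=.35, c'=-.3, loadings .5, r=.7 | -.61 | -.17 |
| b=.35, c'=-.3, loadings .3, r=.7 | -.61 | -.26 (simulated -.25) |
| b=0, c'=0, loadings .5, r=.7 | 0 | +.13 (simulated +.12) |
| b=0, c'=0, loadings .3, r=.7 | 0 | +.04 |

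All rows but the last were also simulated (three arms of 33, 4,000 runs, one follow-up, least squares, two-sided .05) and agree with the algebra to about .01. In the fourth row power is .79 for the condition-only model and .13 for the joint model. In the sixth row the rejection rate is .04 and .07.

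**When each outcome occurs.** The joint coefficient is zero under full mediation (c'=0) with no common cause. Without a baseline covariate, it changes sign only when .89 g lam exceeds the size of a beneficial c'. For c'=-.3 that needs g lam above .3/.89 = .34, or loadings of about .58 each; a baseline covariate raises the bar. In the two rows with c'=-.3, about 27% and 42% of the simulated total effect remains (.166/.611 and .254/.609), with the same sign.

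The calculation covers lab drinking only. Field drinking would add a further mediated path if lab condition affects it. If not, it would act more like an extra proxy for U and shrink the common-cause term.

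**The case against.** The strongest reply is that the text lists predictors and never says they share a model. For Exploratory Aim 3 the plan says outright that measures go into the same models and that condition is a covariate; here the only named covariates are the baseline outcome and sex. Testing each predictor in turn with those covariates is a possible reading, and it would include the condition-only model. This stands in part: joint entry is an inference. It remains the more natural one, because the plan names separate models explicitly for the eBAC and drinks versions and again for Exploratory Aim 2, and does not do so for condition versus drinking. If separate tests were intended, the text should say so.

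Second, the planned baseline covariate matters. Leaving it out would overstate the spurious effect: with loadings of .5 and no lasting effect, the simulated bias is .22 SD with a rejection rate of .13, against .12 SD and .07 with a baseline correlated .7. This stands, so the conclusion rests on the adjusted figures.

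Third, the aim is exploratory, framed as prediction and carries no directional hypothesis; the study is powered for the primary and secondary aims only. This also stands and limits the importance of the point.

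A reader might further infer that a working app would look ineffective in the long run. The documents do not support that. All participants receive the experimental app after the lab sessions, so even a condition-only model compares lab-assigned versions among people who have since had the same app. Nor do they tie the planned grant application to this aim: the abstract and background link it to the lab and field results.

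**Conclusion.** The point holds as a defect of specification in an exploratory analysis. On the natural reading, the condition coefficient at 6 and 12 months is at best a direct effect, open to bias from common causes of lab and later drinking; adjusting for the baseline outcome reduces that bias without removing it.

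A reader might conclude that joint entry necessarily removes or reverses the condition effect. That is too strong: attenuation with the same sign is equally possible, and the documents contain no values that would settle which occurs. The size is therefore a range, from a modest spurious shift of about .04 SD (loadings .3, no lasting effect) to loss of most of a real effect (-.61 to -.17 SD), complete removal, or reversal. It rests on d=.89 from the plan, on the assumed slopes, loadings and baseline correlation, and on a linear model with one follow-up.

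No primary or secondary conclusion changes.

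**What to change.** Divide Exploratory Aim 1 into two stated sets of models, in both Specific Aims and Data analyses:

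1. For each outcome, a model with condition, the baseline report of that outcome and sex, and no drinking measured after randomisation. Report its condition coefficient as the randomised effect of lab-assigned app version at 6 and 12 months, noting that everyone had the experimental app in the field period.
2. Separate prediction models with lab drinking (eBAC or number of drinks) and field drinking as predictors. Keep condition as a covariate and state that its coefficient is not interpreted as an app effect.

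The cost is a few sentences and one extra model per outcome. No new data are needed, and the prediction question is kept in full.
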